was used to monitor real-time cardiac performance throughout the whole procedure. Minute ventilation was adjusted to maintain end-tidal CO₂ 40 ± 5 mmHg, confirmed by serial arterial blood gas analyses. After achieving anticoagulation (activated clotting time >350 seconds) by intravenous administered heparin 300 U/kg prior to cannulation, standard hypothermic CPB (Sarns 8000, Terumo, Ann Arbor, MI) with an extracorporeal membrane oxygenator (Capiox®SX 18, Terumo, Ann Arbor, MI) were carried out in sequence to maintain the body temperature at 26-30 °C during surgery. The perfusionist adjusted the pump flow to obtain an adequate output of 2.2 l/m² of body surface area and adjusted sevoflurane concentration on the vaporizer, to keep mean arterial blood pressure 50-80 mmHg.

Treatment protocol

Before rewarming, the patients were randomly assigned to NTG group with NTG infusion 1-5 mcg/kg/min or control group with 0-0.1 mcg/kg/min. The infusion rate would be tapered if there was profound hypotension (mean arterial pressure <40 mmHg) or cerebral desaturation (absolute saturation value <60 or relative drop to <80% of baseline value each side). Following standard rewarming and deaerating, the pump flow was reduced to 0.5 l/min for release of aortic clamp and was weaned with routine inotropic support, including dopamine 3-8 mcg/kg/min and additional dobutamine, epinephrine, or norepinephrine infusion for acceptable cardiac output. Further intra-aortic balloon pump or extracorporeal membrane oxygenation would be applied for cardiopulmonary support, if needed. Heparin effect was neutralized with protamine sulfate after stop of bypass. All patients were transferred to the cardiovascular surgical intensive care unit (ICU) with endotracheal intubation after the operations were finished. According to the routine criteria, extubation was performed after obtaining oriented consciousness, normothermia (patient rewarmed and shivering controlled), and hemodynamic stability with no uncontrolled arrhythmias and no excessive bleeding (as defined by loss of < 100 ml/h).

2016-0504-v2 - 3 -

Data collection

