Arterial blood gas analysis was routinely examined perioperatively, including before incision, after heparin administration, before aortic unclamping, after aortic unclamping, after protamine administration, and immediately upon ICU admission by GEM Premier 3000 (Instrumentation Laboratory, Lexington, MA, USA), including plasma lactate (detectable limit, 0.3 to 20 mmol/L) and glucose (detectable limit, 20-500 mg/dL) levels. The activated clotting (or coagulation) time was tested by ACT Plus (Medtronic, Minneapolis, MN, USA) after heparin administration, during CPB, after protamine administration, and before the end of surgery (if needed). The perioperative variables were collected, including acid-base status, glucose level, and urine output. Postoperative inotropic use, time to extubation, lengths of ICU and hospital stay, and 30-day mortality were also recorded from the hospital's registry database.

Statistical analysis

All values were expressed as mean \pm SD or number unless otherwise stated. The Student t-test was applied to compare means of continuous variables. Pearson's Chi-square test or Fisher's exact test was used for categorical variables. All statistical tests were two-tailed, with the level of significance set at P values <0.05. Data analysis was performed using the SPSS for Windows.

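### Does taking 30-day mortality from the hospital's registry, and comparing it only by a chi-square or Fisher test, leave the trial unable to report deaths properly?

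*Combined protocol and SAP*

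**What the plan says.** In the combined protocol and SAP, the Data collection section ends with a list of postoperative items: inotropic use, time to extubation, lengths of ICU and hospital stay, and deaths to day 30. On the last it says "and 30-day mortality were also recorded from the hospital"'s registry database. It mentions no day-30 visit, telephone call or linkage to death records, and no rule for a patient whose status at day 30 is unknown. It does not describe what the registry covers.

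The Statistical analysis section gives the comparison: "Pearson's Chi-square test or Fisher's exact test was used for categorical variables". It adds "All statistical tests were two-tailed, with the level of significance set at P values <0.05". Values are to be shown as mean and standard deviation, or as a number, so deaths would appear as a count in each arm. No risk difference, risk ratio or confidence interval is planned for any outcome.

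The document states no sample size, allocation ratio, expected mortality, margin or power. It does not call mortality a primary, secondary or safety outcome, and it states no hypothesis about death.

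**The concern.** Two things look wrong.

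- **Ascertainment.** Length of hospital stay is itself recorded, so discharge times vary and some patients may leave before day 30. If the registry holds only what happens inside the hospital, a patient who dies elsewhere on, say, day 20 would be counted as alive. The outcome would then really be in-hospital mortality under a 30-day label.
- **Analysis.** Death is rare, and a significance test on a handful of events says little. If the report gave only a P value above 0.05, a reader could take it as evidence that the infusion does not raise mortality, when the data could not exclude a sizeable excess. A risk difference with an interval would show that directly.

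At stake is whether the trial's account of deaths is complete, and whether it could mislead about harm.

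**Working it through.** **Inputs.** The document gives only the two-sided 0.05 level and the choice of tests. There is no stated figure to reproduce. Arm sizes, equal allocation and all mortality rates below are assumptions.

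**1. Power of the test.** Power is the sum, over all pairs of death counts (i, j), of Bin(i; n, p1) × Bin(j; n, p2) for the pairs with P < 0.05.

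| Assumed rates | Patients per arm | Fisher | Uncorrected chi-square |
|---|---|---|---|
| 2% vs 6% | 50 | 3.2% | 14.2% |
| 2% vs 6% | 100 | 17.1% | 27.6% |

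For a doubling of mortality, Fisher's power is:

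| Assumed rates | 25 per arm | 50 | 100 | 200 |
|---|---|---|---|---|
| 1% vs 2% | 0.0% | 0.03% | 0.6% | 4.5% |
| 2% vs 4% | 0.02% | 0.6% | 4.4% | 13.1% |
| 5% vs 10% | 1.3% | 6.3% | 19.0% | 40.6% |

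Reaching 80% power with the pooled chi-square test, without continuity correction, would take 1,141 per arm for 2% vs 4%, or 435 for 5% vs 10%. Low power for deaths is therefore a feature of any trial of the assumed sizes, whatever method is chosen.

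**2. What an interval would add.** The Newcombe interval for d = p1 − p2, built from Wilson limits (l, u) in each arm, is

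- lower = d − √[(p1 − l1)² + (u2 − p2)²]
- upper = d + √[(u1 − p1)² + (p2 − l2)²]

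For 1/50 vs 1/50, the Wilson limits are 0.0035 and 0.1050 in both arms. The half-width is √(0.0165² + 0.0850²) = 0.087, so the interval is −8.7 to +8.7 points, with Fisher P = 1.0.

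For 4/100 vs 1/100, the Wilson limits are 0.0157 to 0.0984 and 0.0018 to 0.0545.

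- Lower: 0.03 − √(0.0243² + 0.0445²) = −0.021
- Upper: 0.03 + √(0.0584² + 0.0082²) = +0.089

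The interval is −2.1 to +8.9 points, with Fisher P = 0.37.

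The only inputs are deaths and patients per arm. The interval can be computed by anyone who has those numbers.

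**3. Effect of missed deaths.** Suppose the registry catches a share s of deaths, the same in both arms. The observed rates are s × p1 and s × p2. The risk ratio is unchanged and the difference shrinks by the factor s. For 5% vs 10% at 100 per arm (normal approximation):

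| s | Observed rates | Difference | Power |
|---|---|---|---|
| 1.0 | 5% vs 10% | 5 points | 26.7% |
| 0.8 | 4% vs 8% | 4 points | 22.0% |
| 0.6 | 3% vs 6% | 3 points | 17.4% |

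When true mortality is equal, the observed rates stay equal too, so equal under-capture creates no false difference. The document gives no information on s, which may be 1.

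**4. Does the plan draw the feared conclusion?** The two sections together give a source, a count, a test and a significance level. Neither contains an equivalence claim, a non-inferiority margin or a statement about safety.

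**The case for a change.** The strongest case for acting is that harm is a real question here and the remedy is cheap. The infusion range in the active arm is one labelled for intraoperative hypotension, and the Treatment protocol section has it tapered for low pressure or cerebral desaturation. Death to day 30 is the only mortality outcome recorded. One line on the interval and one sentence on ascertainment would cost no patients and alter no treatment.

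The plan also gives no rule for choosing between its two tests, and the choice can matter. With 4/50 vs 0/50, uncorrected chi-square gives P = 0.041 and Fisher gives P = 0.117.

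Part of this stands. The plan is silent on how day-30 status is known after discharge, and it plans no effect estimate. The point about the choice of test is weaker than it looks. With four deaths in two equal arms, the expected count is 4/2 = 2 per arm, below the usual threshold of 5, so an analyst following ordinary practice would use Fisher. With equal arms, the same holds for any total below ten deaths.

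The rest depends on things the document does not say. A registry may hold vital status from clinic visits or linked records, and the field is named as 30-day mortality. Renaming it in-hospital mortality could introduce an error where none exists. Replacing the test by an interval, instead of showing both, is a preference. The absence of intervals applies to every outcome in the plan and is not a fault in the handling of deaths in particular.

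**Conclusion.** No change to the plan is needed. The reading of the text is right: the registry is the only named source for deaths to day 30, and the only planned comparison is a P value alongside counts. The arithmetic is also right: Fisher's power is 3.2% or 17.1% for 2% vs 6% at 50 or 100 per arm, and intervals run from about ±9 points down to a few points. Every arm size and rate behind those figures is assumed, so they show only that a small trial says little about mortality.

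Following the plan as written gives counts as complete as the registry and, with Fisher's test for sparse counts, a valid P value. It commits nobody to a conclusion about mortality. The interval is a reporting addition that alters no result and can be derived from the counts. How status was established after discharge is a missing detail that one sentence in the report would settle. If capture were incomplete but equal between arms, the risk ratio would be unaffected and the difference would shrink in proportion.

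This view would change if the registry were shown to stop at discharge or to capture deaths differently by arm, or if the trial claimed safety from a non-significant mortality test. The document supports none of these.

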This study was registered with ClinicalTrials.gov as NCT01901419 after obtaining approval of Tri-Service General Hospital Institutional Review Board (TSGHIRB-1-102-05-049). Patients receiving elective cardiac surgery with cardiopulmonary bypass were recruited and signed the written informed consent. Those with complicated comorbidities were excluded, such as chronic hepatic or renal insufficiency, or acute cardiopulmonary failure requiring mechanical ventilation, intra-aortic balloon pump, or extracorporeal membrane oxygenation. Patients were randomly assigned to receive either NTG infusion 1-5 mcg/kg/min (NTG group), the dose labelled to maintain intraoperative hypotension, or 0-0.1 mcg/kg/min (control group), the dose labelled for acute cardiac insufficiency, during rewarming of hypothermic CPB. Those undergoing normothermic CPB decided by the surgeon intraoperatively were not analyzed.

Anesthesia and cardiopulmonary bypass

Routine physiologic monitoring, including three-lead electrocardiogram, pulse oximetry and an invasive arterial blood pressure monitoring were set up immediately before anesthesia induction. In addition, cardiac output was continuously monitored (FloTrac; Edwards Lifesciences, Irvine, CA, USA). Cerebral oximetry (Fore-Sight oximeter; CASMED, Branford, CT, USA), based on near-infrared spectroscopy technology, was applied on the forehead until the end of surgery.

All patients received general anesthesia with midazolam 5 mg, fentanyl 1.5-3.0 mcg/kg, propofol 0.5-1.5 mg/kg, and cisatracurium 0.1-0.2 mg/kg for induction, as well as sevoflurane or isoflurane for maintenance after tracheal intubation. A pulmonary artery catheter (Swan-Ganz Thermodilution catheter 7.5 Fr; Edwards Lifesciences, CA, USA) was placed through right internal jugular vein for postoperative monitoring. Transesophageal echocardiography

2016-0504-v2 - 2 -

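### No baseline adjustment is described for lactate, glucose and acid-base values although a pre-incision sample is routine: a minor loss of precision, not an invalid test

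*Combined protocol and SAP*

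**What the plan says.** The Statistical analysis section covers continuous variables in one sentence: "The Student t-test was applied to compare means of continuous variables". Tests are two-sided at 0.05. No covariate, change score, ANCOVA or repeated-measures model is mentioned. The section does not say at which sample the test is applied, or whether to raw values or to changes.

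The Data collection section lists the sampling times: "Arterial blood gas analysis was routinely examined perioperatively, including before incision, after heparin administration, before aortic unclamping, after aortic unclamping, after protamine administration", and finally ICU admission. These samples include lactate and glucose; acid-base status is also collected.

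The order of events comes from three other places:

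- Anesthesia and cardiopulmonary bypass: anticoagulation is achieved "by intravenous administered heparin 300 U/kg prior to cannulation".
- The opening paragraph on recruitment and randomisation: the infusion is given "during rewarming of hypothermic CPB".
- Treatment protocol: "Before rewarming, the patients were randomly assigned to NTG group", and later "Following standard rewarming and deaerating, the pump flow was reduced to 0.5 l/min for release of aortic clamp".

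**The concern.** The trial routinely collects a baseline value of each laboratory variable before treatment, and the described analysis makes no stated use of it. A pre-treatment value of the same variable is usually the most natural covariate. Leaving it out can widen the confidence interval for the treatment difference. It also leaves a fraction rho (in SD units) of any chance baseline imbalance in a comparison of raw values. What is at stake is the precision of the between-arm differences in lactate, glucose and acid-base variables. Variables without a baseline value, such as time to extubation and length of stay, are not affected.

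**Working it through.** **Which samples are baselines.** Heparin precedes cannulation, and so bypass and rewarming. The before-incision and after-heparin samples therefore both precede the infusion and, on the natural reading of the Treatment protocol, randomisation. The after-unclamping, after-protamine and ICU-admission samples are clearly post-treatment, because clamp release follows rewarming. The before-unclamping sample may fall before or after the start of the infusion; the documents do not say.

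**Inputs.** The documents supply only the two-sided 0.05 level. They give no sample size, SD, effect size or correlation, so there is no stated figure to reproduce. Assumed: rho of 0.2, 0.3, 0.5 and 0.7; equal SDs at baseline and outcome; n = 20 per arm for illustration; 80% power for the raw-value t-test.

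**1. Test on raw post-treatment values.** The ANCOVA variance relative to the t-test is 1 − rho². Allowing for estimation of the slope, it is (1 − rho²) × (1 + 1/(2n − 4)); with n = 20 the second factor is 1 + 1/36 = 1.028. Power is Φ((1.960 + 0.842)/√(1 − rho²) − 1.960).

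| rho | 1 − rho² | Variance cut | Net ratio, 20 per arm | Net cut | Power, from 80% |
|---|---|---|---|---|---|
| 0.2 | 0.96 | 4% | 0.987 | 1% | 81.6% |
| 0.3 | 0.91 | 9% | 0.935 | 6% | 83.6% |
| 0.5 | 0.75 | 25% | 0.771 | 23% | 89.9% |
| 0.7 | 0.51 | 49% | 0.524 | 48% | 97.5% |

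The power column uses 1 − rho² without the slope allowance.

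**2. Break-even.** Setting the net ratio to 1 gives rho = √(1/(2n − 3)): 0.24, 0.16, 0.13 and 0.10 at 10, 20, 30 and 50 per arm. Below that, adjustment gains nothing. At rho = 0 it costs 1/(2n − 4), which is 2.8% at 20 per arm and 1.8% at 30; simulation gives about 2% at both sizes.

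**3. Test on changes from baseline.** With equal SDs the change has variance 2(1 − rho) in units of the outcome variance, so the ANCOVA ratio is (1 − rho²)/(2(1 − rho)) = (1 + rho)/2. For the same four rho values this is 0.60, 0.65, 0.75 and 0.85, before the slope allowance. Here the gain from ANCOVA is largest when rho is low, the reverse of the raw-value case.

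**4. Validity of the t-test.** Under the null, with 20 and 50 per arm, rho from 0 to 0.7 and 40,000 trials per setting, the simulated type I error was 4.8% to 5.0% for normal data and 4.5% to 5.0% for log-normal data.

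**5. Conditional on a chance baseline imbalance (raw values).** If the baselines differ by z standard errors, the null test statistic is approximately N(rho·z, 1 − rho²).

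| rho | z at which the rate passes 5% | Rate at z = 1.5 | Rate at z = 2 |
|---|---|---|---|
| 0.2 | 1.00 | 5.6% | 6.4% |
| 0.3 | 1.01 | 6.2% | 8.1% |
| 0.5 | 1.04 | 8.2% | 13.4% |
| 0.7 | 1.12 | 10.1% | 21.6% |

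Below the crossing point the rate is under 5%, and the average over all trials is 5%.

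**The case against.** The strongest reply is that this is a preference. An unadjusted comparison of randomised groups is acceptable, nothing in the plan contradicts itself here, and no size for the gain can be taken from the documents. Validity is conceded in full. The reply does not remove the point: the data are already collected, and the possible loss from adjusting is about 2% to 3% of variance at 20 to 30 per arm.

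Two parts of the reply stand. First, the documents do not name lactate, glucose or acid-base values as efficacy outcomes. They name no primary endpoint or time point at all, and that gap matters more than this one. Second, the past tense of the Statistical analysis section ("Data analysis was performed using the SPSS for Windows") suggests a finished analysis. Adjusted results would then be further unplanned P values and must be labelled so.

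A reader might infer that the t-test is biased or has an inflated false-positive rate. The calculations do not support this: randomisation keeps it unbiased, and its error rate over all trials is 5%. A reader might also infer that an imbalance matters only at 2 standard errors. That is wrong as well, since the conditional rate passes 5% at about 1 standard error. Neither fact makes the test invalid.

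**Conclusion.** The point holds as a minor improvement in efficiency, worth considering. The analysis section describes no baseline adjustment, a clean pre-treatment value exists, and the cost of not using it is precision only.

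On raw values the net gain is 1% to 48% of variance for rho 0.2 to 0.7 at an assumed 20 per arm, and nil below a rho of about 0.16 at that size. It is probably at the low end, because hypothermic bypass lies between the baseline and every post-treatment sample; that is a judgement, since the documents give no correlation. It may be nil for CO₂-dependent values, because the anaesthesia section says "Minute ventilation was adjusted to maintain end-tidal" CO₂ at a target, which would weaken the link between early and late readings. If the test is on changes, the ratio (1 + rho)/2 applies instead, and the raw-value figures should not be quoted. A reader might infer from the rho = 0.7 row that the trial loses half its information; nothing in the documents supports so high a correlation.

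**What to change.** For lactate, glucose and the acid-base variables, at each clearly post-treatment sample (after unclamping, after protamine, ICU admission), use ANCOVA with the same variable's pre-incision value as covariate. Alternatively, fit one mixed model per variable with treatment, time, treatment-by-time, baseline and baseline-by-time. The last term is needed because the correlation with baseline may differ between unclamping and ICU admission. Report the adjusted between-arm difference with its 95% CI.

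The pre-incision value is preferable to the after-heparin value because it precedes surgery, and so the infusion, whatever the exact moment of randomisation. The before-unclamping sample should not serve as baseline, and should be an outcome only if it follows the start of the infusion. State also whether the existing t-tests use raw values or changes, and at which samples.

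This needs no new patients or data, and the SPSS package that the plan names can fit both models. If the analysis is still open, it takes a few lines of text. If it is complete, keep the t-tests and set the adjusted results beside them, labelled post hoc. The statistical downside is the variance inflation of about 2% to 3% at 20 to 30 per arm if rho is near zero.

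### Does the plan need changing because its single Student t-test rule does not say how deaths before extubation or discharge count in the duration outcomes?

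*Combined protocol and SAP*

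**What the plan says.** The Data collection section lists the outcomes in question: "Postoperative inotropic use, time to extubation, lengths of ICU and hospital stay, and 30-day mortality were also recorded". The source is the hospital's registry database.

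The Statistical analysis section treats all continuous data alike. Values are summarised as mean with "SD or number unless otherwise stated", and "The Student t-test was applied to compare means of continuous variables". Tests are two-sided at 0.05. Nothing else is stated for durations, and the only exclusion from analysis, for normothermic bypass in the opening paragraph on recruitment, has nothing to do with death.

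The Treatment protocol section shows why death matters for the first duration: "All patients were transferred to the cardiovascular surgical intensive care unit (ICU) with endotracheal intubation after the operations were finished", and "extubation was performed after obtaining oriented consciousness, normothermia" together with the other recovery criteria. A patient who dies intubated therefore has no extubation time.

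The recruitment paragraph also bears on how many deaths to expect: "Patients receiving elective cardiac surgery with cardiopulmonary bypass were recruited and signed the written informed consent". It excludes patients with chronic liver or kidney impairment and those already on ventilatory or mechanical circulatory support.

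**The concern.** Death cuts a stay short or leaves it without an end. If deaths are counted at their observed length, early deaths shorten the mean, and an arm that loses more patients early can appear to recover faster. If deaths come after a long stay, that arm looks slower. If deaths are dropped, the comparison is no longer between the groups as randomised. A rule chosen after the data are seen could move the result.

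For time to extubation the stated test cannot be run on a patient who dies intubated unless someone makes a choice the plan does not make. There is also a smaller point about power: durations of this kind are often right-skewed, and a t-test on raw days then loses power against a rank test.

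**Working it through.** The plan states no sample size, event rate, mean or SD, so there is no figure of its own to reproduce. Everything below rests on assumed inputs.

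**Formula.** Let m be the survivors' mean, equal in both arms, p the proportion who die before the event and d their mean day of death. With deaths counted at observed length,

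bias = p1 × (d1 − m) − p2 × (d2 − m).

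With the same d in both arms this is (p1 − p2) × (d − m). It is zero at d = m and changes sign there, so the direction is not fixed. If p1 = p2 and d1 = d2 it is zero.

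**Assumed durations (log-normal).**
- Hospital stay, median 13 days, log-SD 0.5: m = 13 × exp(0.125) = 14.7.
- ICU stay, median 3, log-SD 0.6: m = 3 × exp(0.18) = 3.6.
- Time to extubation, median 1, log-SD 0.6: m = 1 × exp(0.18) = 1.2.

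**Bias in days for the arm with more deaths.** The multipliers are 0.06, 0.03 and 0.01. The last column is the simulated one-sided error of the t-test at 8% against 2% with 100 per arm and exponential death times (nominal 2.5%).

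| Duration | d − m | 8% v 2% | 5% v 2% | 3% v 2% | Error, 8% v 2% |
|---|---|---|---|---|---|
| Hospital, d = 3 | −11.7 | −0.70 | −0.35 | −0.12 | 9.1% shorter |
| Hospital, d = 20 | +5.3 | +0.32 | +0.16 | +0.05 | 3.8% longer |
| ICU, d = 3 | −0.6 | −0.04 | −0.02 | −0.01 | 3.1% shorter |
| ICU, d = 10 | +6.4 | +0.38 | +0.19 | +0.06 | 9.8% longer |
| Extubation, d = 0.5 | −0.7 | −0.04 | −0.02 | −0.01 | 5.5% shorter |
| Extubation, d = 3 | +1.8 | +0.11 | +0.05 | +0.02 | 8.5% longer |

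Across repeated simulations of this kind, the one-sided error was at most about 5.5% at 5% against 2% and at most 3.4% at 3% against 2%. With 50 per arm the hospital day-3 error falls from 9.1% to 6.8% (8% against 2%), and is 4.1% at 5% against 2%.

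**Where larger errors arise.**
- *Different timing, equal mortality.* Mean death day 3 against 20 for hospital stay, 5% in each arm: 0.05 × (3 − 20) = −0.85 day by formula, −0.82 simulated, with 9.5% error. At 2% in each arm it is −0.34 day and 4.6%.
- *Deaths dropped, 8% against 2%, hospital stay.* Deaths unrelated to stay: no bias, 2.5%. Deaths from the longest half: −0.37 day, 5.2%. Deaths from the longest fifth: −0.81 day, 11.2%. The last case needs 0.08/0.20 = 40% of that fifth to die in one arm.
- *All deaths very late.* ICU stay with survivor mean 4 and SD 2, and every death at exactly day 20: at 5% against 2%, 0.03 × (20 − 4) = +0.48 day, with 8.6% error at 50 per arm and 15.3% at 100. Here the arm with more deaths looks worse, and its patients did occupy the ICU longer. With every death at day 1, the direction that would flatter a harmful arm, the bias is 0.03 × (1 − 4) = −0.09 day and the error 4.0% and 5.2%.

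**What p means.** It is the proportion dying before the particular event, not 30-day mortality. Deaths while intubated, or in the ICU, may be well below 30-day mortality. Using one rate for all three durations then overstates the extubation row most.

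**The alternative test.** With hospital stay, 8% against 2%, death day 3 and 100 per arm, a worst-rank Wilcoxon test reduces the false finding of a shorter stay to 0.4%; a plain rank test leaves it at 9.9%. But with equal stay in survivors, worst rank is significant against the higher-mortality arm in 11% of trials (7.4% at 50 per arm), and in about 5.5% at 5% against 2%.

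**Skew.** For a 30% shorter stay with 50 per arm, t-test against rank-test power is 91 v 93% at log-SD 0.5, 77 v 82% at 0.6, 48 v 57% at 0.8 and 29 v 40% at 1.0. Type I error of the t-test stays at 4.2 to 5.1%. Any material gain depends on skew that the documents do not report.

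**The case for a change.** The best argument for a change is that the gap is real and cheap to close. Deaths are foreseen: 30-day mortality is collected, and the Treatment protocol section allows mechanical support after weaning if needed. Two sentences would settle how such patients are counted and remove a choice that could otherwise be made with the results in view. The sign of the bias cannot be predicted, so a reader cannot correct for it without knowing the rule.

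Most of this stands. No rule is written, the direction is open, and for a patient who dies intubated the t-test cannot be applied as described. Two parts do not carry over into a required change.

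First, only time to extubation lacks a value at death. ICU and hospital stay have an observed length, and counting it up to death is an ordinary reading.

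Second, there is no single better rule to write in. Worst rank merges death with duration, so a significant result no longer speaks about days. Cumulative incidence with death as a competing event, and days alive and free of ventilation or hospital, answer other questions again. Choosing among them is a matter of preference. The case for a rank test rests on assumed skew.

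It would be wrong to dismiss the point on the ground that these outcomes are secondary: the documents name no primary outcome.

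**Conclusion.** The plan has a gap in detail but no demonstrated fault. If deaths before the event are few and roughly balanced, which is plausible though not documented for this elective population, the distortion is small: at 3% against 2%, the largest shift tabulated is 0.12 day on a 14.7-day stay. Counting up to death then gives close to the nominal error. Dropping deaths does so when they are unrelated to stay.

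The gap is one analysts fill sensibly: count ICU and hospital stay to discharge or death, give time to extubation among those extubated, and show deaths by arm alongside. Mortality is already recorded and falls under the plan's rule for categorical data. It does not by itself show whether death came before extubation or discharge; that has to be read from the registry record.

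This conclusion rests on deaths before the event being uncommon and not grossly different between arms in number or timing. If the trial saw something like 8 deaths against 2 per 100, the durations could not be read without the mortality comparison, whatever test was used.

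### Should the plan have named Welch's unequal-variance t-test instead of Student's t-test for continuous outcomes?

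*Combined protocol and SAP*

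**What the plan says.** Under Statistical analysis, the combined protocol and SAP states: "The Student t-test was applied to compare means of continuous variables". It adds: "All statistical tests were two-tailed, with the level of significance set at P values <0.05". It does not name a variance version (pooled or Welch), a variance check or a confidence interval. Results are to be reported as means with SDs.

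On allocation, the Treatment protocol section says "the patients were randomly assigned to NTG group with NTG infusion 1-5 mcg/kg/min or control group with 0-0.1 mcg/kg/min". It gives no ratio, blocking or sample size. The opening paragraph adds one exclusion: "Those undergoing normothermic CPB decided by the surgeon intraoperatively were not analyzed". No SD is given for any outcome. The continuous outcomes include some that are probably right-skewed; under Data collection, "time to extubation, lengths of ICU and hospital stay, and 30-day mortality were also recorded".

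**The concern.** The pooled t-test estimates one common variance. If the smaller arm is the more variable one, the pooled standard error is too small and P values are too low. If the larger arm is the more variable one, the opposite happens. A larger trial does not cure this at a fixed split.

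Both conditions look possible here. Without a stated ratio or blocking, and with some patients left out of the analysis, the analysed arms may be unequal. The NTG arm receives a five-fold range of infusion rates with tapering rules, so if the drug acts, its arm could be more variable than control. At stake would be a false-positive rate away from 5% for every continuous outcome, which one added word (Welch) might seem to prevent.

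**Working it through.** **Inputs.** From the document: two-sided 5% level, Student's t-test, two randomised arms. Not in the document, so assumed: N of 100 (with 40 as a range), splits from 50:50 to 60:40, SD ratios of 1.5 and 2, and normal or lognormal data. The plan states no figure on this point, so there is none to reproduce.

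**Step 1: no effect of NTG.** Randomisation makes the two arms samples from the same population. If NTG does nothing to an outcome, both arms have the same mean and the same SD. The pooled test's equal-variance assumption then holds whatever the arm sizes. For its false-positive rate to be wrong, NTG would have to change the spread of an outcome and leave its mean exactly unchanged.

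**Step 2: equal arms.** The squared pooled standard error has expectation

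[((n1−1)·s1² + (n2−1)·s2²)/(n1+n2−2)]·(1/n1 + 1/n2),

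and the true squared standard error is s1²/n1 + s2²/n2. With n1 = n2 the two are identical. Only the degrees of freedom differ between the tests, and the simulated Student error at 50+50 is 5.1% for both SD ratios (0.0505 and 0.0511).

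**Step 3: unequal arms and unequal spreads.** Take 45+55 with the smaller arm more variable and SD ratio 1.5 (variances 2.25 and 1):

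- Pooled: (44·2.25 + 54·1)/98 = 153/98 = 1.561; times (1/45 + 1/55) = 0.0404 gives 0.0631.
- True: 2.25/45 + 1/55 = 0.0500 + 0.0182 = 0.0682.
- Ratio of standard errors: √(0.0631/0.0682) = 0.962.

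The pooled standard error is about 4% too small. Simulated Student errors for normal data with equal means at N=100 (Welch 5.0% throughout):

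| More variable arm + other arm | SD ratio 1.5 | SD ratio 2 |
|---|---|---|
| 45+55 | 6.0% | 6.6% |
| 55+45 | 4.2% | 3.8% |
| 40+60 | 7.0% | 8.3% |
| 60+40 | 3.5% | 2.8% |

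The error goes either way, depending on which arm is more variable. The document does not settle that.

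**Step 4: how likely such splits are.** Under simple 1:1 randomisation the arm size is Binomial(N, 0.5). A split of 60:40 or worse, in either direction, has probability 5.7% at N=100 and 26.8% at N=40. Averaging the Student error over this distribution gives, for SD ratios 1.5 and 2:

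- N=100: 5.08% and 5.22%
- N=40: 5.24% and 5.50%

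The excess over 5% is therefore 0.1 to 0.5 points.

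**Step 5: skewed outcomes.** Lognormal data with equal means and a coefficient of variation of 0.5 in the less variable arm, N=100:

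| More variable arm + other arm | SD ratio | Student | Welch |
|---|---|---|---|
| 40+60 | 1.5 | 7.1% | 5.8% |
| 40+60 | 2 | 9.1% | 7.0% |
| 45+55 | 2 | 7.7% | 6.7% |
| 55+45 | 1.5 | 4.6% | 5.1% |
| 55+45 | 2 | 5.1% | 5.9% |

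Welch reduces the error in some rows but does not restore 5%. In the last row it is further from 5% than Student.

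**The case for a change.** The strongest case for the change is that Welch's test costs almost nothing. With equal SDs and an 80% power design, the loss is 0.05 points at 55:45 and 0.15 at 60:40 (N=100), and about 0.5 at 24+16. It reaches 2 to 3 points only in extreme splits such as 80+20 or 30+10. For normal data Welch holds 5% in every setting examined. Naming the version would also remove a choice the analyst could make after seeing the data. And if NTG does work, Step 1 no longer protects the pooled analysis: intervals from it could cover less than 95% (93.4-94.0% at 55:45 with the smaller arm more variable).

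The figures stand, and Welch is a reasonable default for someone drafting a new plan. But the coverage argument concerns confidence intervals that the Statistical analysis section does not plan; it plans means, SDs and P values. The case for imbalance is also thin. Assignment came late ("Before rewarming, the patients were randomly assigned to NTG group"), so the surgeon's decision for normothermic bypass may well have preceded it. In that case the exclusion would not unbalance the arms, although the document does not make the order explicit. Finally, the analysis text is in the past tense, so changing the name alone would misdescribe the tests unless every comparison were re-run.

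**Conclusion.** The concern does not hold as a criticism of this plan. Student's t-test is a standard, valid comparison of two randomised arms. It is correct when NTG has no effect on the outcome and close to nominal when the arms are equal. Under simple 1:1 randomisation and SD ratios of 1.5 to 2, the average excess over 5% for normal data is 0.1 to 0.5 points at N=100 to 40. Errors of 7.0-8.3% need a 60:40 split and a markedly more variable smaller arm at once, and the document shows neither. For skewed outcomes the alternative is not reliably better.

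N, the split, the SD ratios and the distributions are all assumptions, because the document gives none of them. Evidence of a deliberately unequal allocation, or of clearly different spreads, would reopen the question. How skewed outcomes should be analysed is a separate matter, which choosing between Student and Welch does not settle.
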